8.2.12 Pulse Oximetry

Oxygen saturation at screening will be summarized for the OTL-101 treated subjects using descriptive statistics.

8.2.13 Bone Marrow Harvest

The number (%) of OTL-101 treated subjects with each blood type, for whom harvest can be performed, for whom harvest was performed and with central venous access will be summarized.

Total number of CD34⁺ cells harvested and back-up cells collected will be summarised using descriptive statistics along with the number (%) of OTL-101 treated subjects with each cell type (total nucleated cells / mononuclear cells).

8.2.14 Busulfan Pharmacokinetics

The area under the curve (AUC) for busulfan will be summarised using descriptive statistics for the OTL-101 treated subjects.

8.2.15 OTL-101 Administration

The number (%) of subjects who received OTL-101 will be summarised along with the age in months at transplant and the number of infusions received (1 or 2).

For each infusion, CD34⁺ pre-TD vector copy number (copy/cell), CD34⁺ post-TD vector copy number (copy/cell), CD34⁺ pre-TD ADA enzyme activity (nmol/min/10⁸ cells), CD34⁺ post-TD ADA enzyme activity (nmol/min/10⁸ cells), subject weight (kg), total CD34⁺ cells infused (x 10⁶ cells), total CD34⁺ cells infused / kg, infusion volume (mL), duration of infusion (min) and infusion rate (mL/min) will be summarized using descriptive statistics.

8.2.16 Transplant Details for the HSCT Controls

Age (months) at transplant, number of CD34⁺ cells/kg transplanted and busulfan dose, if appropriate, will be summarized for each HSCT control group using descriptive statistics.

Final Version 4.0 Page 16 of 27

Number (%) of subjects with each type of transplant cells, transplant donor type, conditioning type, receiving enzyme replacement therapy (ERT) prior to the transplant, receiving ERT after the transplant, receiving IgRT prior to the transplant, receiving IgRT after the transplant and receiving gene therapy after the transplant will be summarized for each HSCT control group.

8.2.17 Exposure

Duration of follow-up in months will be calculated for the OTL-101 treated subjects as: 12*(date of final evaluation - date of infusion + 1)/365.25.

For the HSCT controls, the duration of follow-up will be recorded on the eCRF.

Duration of follow-up will be summarized for the OTL-101 treated and the HSCT control groups using descriptive statistics. In addition, the total subject-years of follow-up in each treatment group will be presented.

8.3 Efficacy Evaluations

The primary comparison for all efficacy analyses will be between the OTL-101 treated subjects and the allogeneic HSCT controls treated at either GOSH or Duke University without a matched related donor.

Secondary comparisons will be between:

- the OTL-101 treated subjects and the HSCT controls treated at either GOSH or Duke University with a matched related donor;
- the OTL-101 treated subjects and the total group of HSCT controls.

8.3.1 Primary Efficacy Endpoints

8.3.1.1 Overall Survival at 12 Months

Overall survival will be evaluated using the time in months from transplant to either the subject's death or their last evaluation calculated as:

12*(date of death/last evaluation – date of transplant)/365.25,

or, for HSCT control subjects for whom the dates were not recorded, as:

age in months at death/end of follow-up - age in months at transplant.

The number (%) of subjects who were still alive at 12 months post-transplant will be summarised. For the purpose of this analysis, any subject who withdrew from the study prior to 12 months, who was known to be alive at the last evaluation, will have a status of "unknown". The proportion and exact 95% confidence interval (CI) for survivors at 12 months post-transplant will be calculated for the OTL-101 treated and each of the HSCT control groups along with the difference in proportions (with 95% CI) between the OTL-101 treated and each of the control groups, excluding those with unknown status.

Final Version 4.0 Page 17 of 27

Overall survival in each treatment group will also be presented using a Kaplan-Meier curve for time to death. For the purpose of this analysis, any subject who withdrew from the study prior to 12 months and was known to be alive at the last evaluation will be censored at the date of their last evaluation. If appropriate, the proportion alive at 12 months and the associated 95% confidence interval will be estimated for each treatment group from the Kaplan-Meier curve along with the median survival time (and interquartile range), if they can be estimated from the data.

If there is at least one event in each group, the log-rank test will be used to compare the difference in survival curves between the OTL-101 treated subjects and each of the HSCT control groups.

In addition, a Bayesian analysis will be carried out. The prior distribution for the rate of survivors in each treatment group will be set to Beta(α =1, β =1) (a conservative non-informative prior). The number of survivors in each group (X) will be estimated and the posterior distribution for the rate of survivors in each group will be updated to Beta(α =1 + X, β =1 +N - X), where N is the total number of subjects in the group. Histograms will be presented for the posterior distributions for each treatment group.

A posterior distribution for the difference between the survival rate in the OTL-101 treated group and each of the HSCT control groups will be estimated empirically via simulation with 10,000 replications. Based on the distribution above, posterior probabilities for the following will be calculated:

- rate on OTL-101 > rate on control (superiority like test);
- rate on OTL-101 \geq rate on control -10% (non-inferiority like test).

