8.1.2 Summary of Withdrawals

Number (%) of subjects who completed the study period will be summarised along with the reason for study withdrawal. The denominator for the percentages will be the number of subjects treated.

At the interim look and the primary analysis, the number (%) completing the designated follow-up period and ongoing in the study will also be summarized.

Should any subjects have withdrawn from the study, a listing will be produced for these subjects noting the reason for study withdrawal, and the time since infusion at withdrawal.

Final Version 4.0 Page 12 of 27

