8.3.1.2 Event-free Survival at 12 Months

Event-free survival will be evaluated using the time in months from transplant to either the first event or their last evaluation calculated as:

12*(date of event/last evaluation – date of transplant)/365.25,

or, for HSCT control subjects for whom the dates were not recorded, as:

age in months at death/end of follow-up - age in months at transplant.

For the purpose of this analysis, the events of interest are:

- death:
- reinstitution of PEG-ADA ERT;
- requirement for a second transplant.

Event-free survival will be summarized in the same way as overall survival described in Section 8.3.1.1.

Final Version 4.0 Page 18 of 27

In addition, if there are any events (other than death), the time to each event will be summarized in a similar manner to the overall event-free survival.

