8.3.2 Secondary Efficacy Endpoints

8.3.2.1 Overall and Event-free Survival at 24 Months

Overall and event-free survival at 24 months will be summarized in the same way as for the analyses at 12 months described in Sections 8.3.1.1 and 8.3.1.2.

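### Landmark survival status turns on withdrawal rather than on what is known, and the Bayesian analysis of the same endpoint has no matching exclusion

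*SAP*

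**What the plan says.** SAP 8.3.1.1 treats a subject who leaves early in three ways for one endpoint.

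- **Landmark proportion.** Status at month 12 is *unknown* for "any subject who withdrew from the study prior to 12 months, who was known to be alive at the last evaluation". The proportion, its exact 95% CI and the difference from each control group are then calculated "excluding those with unknown status".
- **Kaplan-Meier.** The same subject "will be censored at the date of their last evaluation".
- **Bayesian analysis.** The posterior is Beta(1 + X, 1 + N − X), "where N is the total number of subjects in the group". X is to be estimated, and no rule is given for unknown subjects.

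SAP 8.3.1.2 carries this over: "Event-free survival will be summarized in the same way as overall survival described in Section 8.3.1.1". SAP 8.3.2.1 does so again: "Overall and event-free survival at 24 months will be summarized in the same way as for the analyses at 12 months".

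Protocol 8.6, 9.10 and 9.11 provide for limited collection, after a subject leaves, of survival, rescue transplant and PEG-ADA reinstatement, up to the end of that subject's expected follow-up. Protocol 11.2 states that every analysis draws on all relevant data that are available. The SAP does not mention the post-exit data.

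**The concern.** The outcomes collected after exit are the components of overall and event-free survival. The *unknown* label nevertheless depends on whether the subject withdrew, not on whether the landmark status is known. Two things follow.

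First, an outcome on file may be left out. If *last evaluation* means the last on-study evaluation, a post-exit event before the landmark is dropped and the reported rate is too high. If it includes post-exit contact, that event counts, but a withdrawer confirmed alive after month 12 still meets the literal definition of *unknown*.

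Second, the proportion excludes unknown subjects while the Bayesian N keeps them. If X counts known survivors, an unknown subject acts as a failure in the second analysis and is absent from the first. Two programmers could both follow the SAP and report different posteriors.

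These are the primary efficacy endpoints, with 20 treated subjects, so one subject moves a rate by 5 percentage points.

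**Working it through.** **Inputs.** OTL-101 N = 20 (protocol 11.4). Controls of any donor type: 25 at GOSH plus 10 at Duke = 35 (protocol Appendix H). The prior is Beta(1,1) and the non-inferiority-like margin is 10 points (SAP 8.3.1.1). The primary comparison is with "allogeneic HSCT controls treated at either GOSH or Duke University without a matched related donor"; the size of that group is not given. The number of withdrawals is not given either, so one is assumed below.

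**The plan's own precision figures (protocol 11.4).** The exact two-sided 95% interval for 19/20 is 75.1% to 99.9%, with half-width (99.9 − 75.1)/2 = 12.4%, which matches the stated 12%. For 20/20 the lower limit is 0.025^(1/20) = 83.2%, with half-width 8.4%. The stated 7% appears only with the full 5% in one tail: 0.05^(1/20) = 86.1%, half-width 7.0%. That is a side observation; the intervals below are two-sided.

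**Landmark proportion, one OTL-101 withdrawer.**

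| Case | Literal SAP rule | Using the collected outcome |
|---|---|---|
| EvFS, PEG-ADA restarted after exit, before the landmark | 19/19 = 100% (82.4 to 100) | 19/20 = 95% (75.1 to 99.9) |
| OS, confirmed alive after month 12 | 19/19 = 100% (82.4 to 100) | 20/20 = 100% (83.2 to 100) |

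The lower limit for 19/19 is 0.025^(1/19) = 82.4%. The first row needs the on-study reading of *last evaluation*; the second arises on either reading.

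**Posterior mean, one unknown OTL-101 subject, the other 19 event-free.** The mean is (1 + X)/(2 + N).

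- X = 19 known survivors, N = 20: 20/22 = 90.9%.
- X = 19, N = 19 (exclusion as in the proportion): 20/21 = 95.2%.
- X = N × S(12) = 20 from Kaplan-Meier, N = 20: 21/22 = 95.5%.

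**Probability that OTL-101 exceeds control.** The OTL-101 posterior is Beta(20,2) if N = 20 and Beta(20,1) if N = 19. The control posterior is Beta(1 + k, 1 + n − k) for k successes among n. All control rates are assumed.

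| Controls, k/n | N = 20 | N = 19 |
|---|---|---|
| 21/35 | 0.998 | 1.000 |
| 23/35 | 0.993 | 0.999 |
| 28/35 | 0.919 | 0.979 |
| 31/35 | 0.728 | 0.901 |

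With the 10-point margin the pairs are 0.999 and 1.000 at 23/35, 0.990 and 0.998 at 28/35, and 0.955 and 0.990 at 31/35.

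The 35 controls belong to a secondary comparison. For the primary group I assumed 10, 15, 20 or 25 controls. With 6, 10, 13 and 16 successes (60% to 67%), superiority is 0.983 to 0.993 with N = 20 and 0.996 to 0.999 with N = 19. At 80% it is 0.89 to 0.91 and 0.96 to 0.98.

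For orientation, Table 1 in protocol 2.1.3.1 (an older series) has 27 + 5 + 21 = 53 of 80 alive (66%), and 5 + 21 = 26 of 50 alive (52%) without a matched sibling or family donor. Near those rates the shift is about 0.01 or less.

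**The other direction.** Suppose OTL-101 is 20/20 and there are 20 controls, 2 with events and 2 lost alive. With X = 16, superiority is 0.976 at N = 20 and 0.902 at N = 18. Keeping lost controls in N favours OTL-101.

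**The case against.** The strongest reply is that the SAP does not bar post-exit data. It measures time to death, event or last evaluation without limiting these to on-study visits, and protocol 11.2 points the same way, so an analyst with a recorded PEG-ADA restart should count it. This stands in part: it answers the lost-event example, but not the withdrawer confirmed alive after month 12.

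A second reply is that protocol 11.6.2.4.1 itself restricts 12-month rates to subjects who have reached that time point, and that a Kaplan-Meier estimate of X would make total N coherent (mean 95.5%). Both are reasonable readings. Neither reconciles the two denominators as written, because the SAP does not say how X is estimated.

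The route is also narrow, and that stands. Withdrawers are asked to continue scheduled evaluations (protocol 8.6, 9.11). Protocol 6.4.1 recommends restarting PEG-ADA by month 12 if any one of its failure criteria is met, and 7.5 restarts it at about month 6 for a complete failure, so most failures would already be on-study events. The main exposure is event-free survival at month 24, for example when gene marking is lost after month 12.

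Finally, protocol 2.1.6.2 reports 100% overall and event-free survival in 18 evaluable patients at the March 2016 cut-off. SAP 8.1.2 would also expose any withdrawal: "a listing will be produced for these subjects noting the reason for study withdrawal, and the time since infusion at withdrawal". That shows the problem but does not correct the estimate.

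**Conclusion.** The concern holds, at minor severity. As written, the *unknown* rule can set aside a landmark status that is known, and the proportion and Bayesian analyses of one endpoint can use different denominators.

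With one affected OTL-101 subject, the event-free rate could read 100% instead of 95%, and the posterior mean could differ by 95.2 − 90.9 = 4.3 points. The shift in the superiority probability is negligible near control rates of 52% to 66%. It is about 0.06 to 0.07 at 80%, and 0.17 at 31/35.

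These sizes assume one withdrawal, X counted as known survivors, and hypothetical control rates and primary-group sizes. The event-free version of the rule is inferred from the cross-reference in SAP 8.3.1.2. If every landmark status is known the effect is nil, and no pre-specified threshold or decision rule depends on the result.

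**What to change.** Amend SAP 8.3.1.1 so that the change carries through to 8.3.1.2 and 8.3.2.1:

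1. Assign 12- and 24-month overall and event-free survival status, with event and censoring dates, from all available data, including data collected after exit. Keep *unknown*, or censoring before the landmark, only where no information reaches the landmark.
2. Use the same subjects for X and N in the Bayesian analysis as in the proportion, that is, those with known status. Apply this to both groups, and state the status of controls whose follow-up is shorter than the landmark.
3. Optionally, add a bounding run with unknown OTL-101 subjects as failures and unknown controls as successes.

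The cost is a few lines of text and a small programming change. Post-exit data are limited, so some statuses may stay unknown, and the OTL-101 estimate may become slightly less favourable.

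Separately, protocol 9.10 allows removal for absent gene marking from month 6, while 8.6 and 11.7.2 place it in the second year or later. These passages should be reconciled.

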11 STATISTICAL CONSIDERATIONS

11.1 Background

The objectives of the statistical analyses described in this section are to demonstrate the safety and efficacy of the fresh formulation of OTL-101, an autologous, genetically modified CD34+ Hematopoietic Stem Cells (HSC) for the treatment of severe combined immunodeficiency due to

adenosine deaminase deficiency (ADA-SCID). Full details of the planned statistical analyses for this study are found in the statistical analysis plan.

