11.6.2.4 Efficacy Analyses

11.6.2.4.1 Primary Efficacy Analyses

The primary efficacy endpoints, overall survival (OS) and event free survival (EvFS), will be analyzed descriptively, including frequencies for each type of event for EvFS. Additionally, the following analyses will be done to present and compare the treatment arms, OTL-101 subject and HSCT historical control groups, so as to provide as complete a picture as possible of efficacy given the small sample size:

1. OS and EvFS will be described using Kaplan-Meier curves for time to death/event by treatment arm, and a comparison between arms made using the log-rank test.

- OS and EvFS rates at 12 months (for those subjects who have reached the 12-month time point) will be described by arm and the difference between arms presented along with associated exact binomial CIs.

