11.6.3 Primary Analysis

The primary analysis will include data from the current study where all subjects have reached the 12-month time point, HSCT historical controls (with or without HLA-matched related sibling donor, evaluated separately and together).

The following analyses will be repeated, as described in preceding sections:

- Subject disposition ([Section 11.6.2.1](#))
- Baseline characteristics ([Section 11.6.2.2](#))
- Safety ([Section 11.6.2.3](#))
- Efficacy ([Section 11.6.2.4](#))

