11.6.4 End of study Analysis

The end of study analysis will repeat the analyses for the preceding section ([Section 11.6.3](#)) for the study cohort in which all subjects are expected to have completed 24 month follow-up.

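### The SAP runs the log-rank test only if each group has an event; the test needs less, and it is dropped if OTL-101 has none

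*SAP*

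**What the plan says.** Protocol 11.6.2.4.1 plans, for overall survival (OS) and event-free survival (EvFS), Kaplan-Meier curves by arm and "a comparison between arms made using the log-rank test". It attaches no condition on the number of events. Protocol 11.6.3 carries this to the primary analysis ("The following analyses will be repeated, as described in preceding sections") and 11.6.4 to the end of the study ("The end of study analysis will repeat the analyses for the preceding section"). Protocol 11.1 leaves the detail to the SAP: "Full details of the planned statistical analyses for this study are found in the statistical analysis plan".

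SAP 8.3.1.1 adds the condition: "If there is at least one event in each group, the log-rank test will be used to compare the difference in survival curves". The sentence goes on to name OTL-101 and each of the HSCT control groups. SAP 8.3.1.2 extends the method to EvFS ("Event-free survival will be summarized in the same way as overall survival"), and SAP 8.3.2.1 extends it to OS and EvFS at 24 months ("will be summarized in the same way as for the analyses at 12 months"). The SAP gives no reason for the condition and names no substitute test.

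The other comparisons in SAP 8.3.1.1 do not depend on it: the difference in proportions with a 95% interval, the Kaplan-Meier analysis, and the Bayesian posterior probabilities.

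**The concern.** A log-rank test cannot be computed when there are no events at all, so some guard is sensible. An empty arm is a different matter. With no OTL-101 events and several control events the statistic is well defined, and the data then favour OTL-101 as strongly as they can. The SAP rule drops the test in that case.

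The case is realistic. Protocol 2.1.6.2 reports 100% OS and 100% EvFS in 18 evaluable OTL-101 patients at the 31 March 2016 cut-off. At stake is the only planned between-group comparison that uses event times. The difference in proportions leaves out subjects of unknown status, the Bayesian comparison works on survivor counts, and the Kaplan-Meier estimates are given group by group.

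**Working it through.** The documents give no event count, power or significance level for the log-rank test, so there is no stated figure to reproduce. The check asks when the test is defined, how likely the condition is to fail, and how accurate the p-value would be.

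**Inputs.** OTL-101 group of 20 (Protocol 11.4). No events in 18 evaluable patients (Protocol 2.1.6.2). Controls: 25 from GOSH and 10 from Duke, all donor types (Protocol Appendix H). The number without a matched related donor, who form the primary comparator, is not given, so sizes of 10 to 25 are assumed. True rates of 95%, 98% and 99% are also assumed. Control events fall at distinct times while all 20 OTL-101 subjects are at risk.

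**1. When the test is defined.** At event time j let n1j be the OTL-101 subjects at risk, nj the total at risk and dj the events.

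- E = Σ dj·n1j/nj
- V = Σ dj·(n1j/nj)·(1 − n1j/nj)·(nj − dj)/(nj − 1)
- chi-square = (O − E)²/V on 1 degree of freedom

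The only requirement is V > 0: at least one event in the pair while both groups have subjects at risk.

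For 0/20 against 5/20:

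- O = 0
- E = 20/40 + 20/39 + 20/38 + 20/37 + 20/36 = 2.635
- V = 0.2500 + 0.2498 + 0.2493 + 0.2484 + 0.2469 = 1.244
- chi-square = 2.635²/1.244 = 5.58, p = 0.018

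With a single control event in 20, E = 0.5, V = 0.25, chi-square = 1.00 and p = 0.317. With no events in either group, V = 0 and the test is undefined.

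**2. How often OTL-101 would have no event.** P(no event in 20) = rate^20: 0.95^20 = 0.358, 0.98^20 = 0.668, 0.99^20 = 0.818.

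**3. Accuracy of the chi-square p-value.** If only controls have events, the one-sided permutation probability that all d events fall among n controls is C(n, d)/C(20 + n, d). With equal groups the opposite extreme is equally likely, so the two-sided value is double.

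- 0/20 v 4/20: C(20,4)/C(40,4) = 4,845/91,390 = 0.0530; two-sided 0.106
- 0/20 v 5/20: C(20,5)/C(40,5) = 15,504/658,008 = 0.0236; two-sided 0.047
- 0/20 v 2/10: C(10,2)/C(30,2) = 45/435 = 0.103. With both events in the OTL-101 group the statistic is smaller than observed, so the two-sided value is also 0.103

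| OTL-101 v control events | chi-square | chi-square p | two-sided permutation p |
|---|---|---|---|
| 0/20 v 4/20 | 4.34 | 0.037 | 0.106 |
| 0/20 v 5/20 | 5.58 | 0.018 | 0.047 |
| 0/20 v 2/10 | 4.22 | 0.040 | 0.103 |

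The test can therefore be computed in all of these cases, but its usual p-value is too small in them.

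**The case against.** The strongest reply is that the documents do not conflict. The protocol names the test in one clause and refers full details to the SAP, and a feasibility condition is such a detail. This stands: a reader might infer that the SAP contradicts the protocol, and Protocol 11.1 does not support that. What remains is that this guard is stricter than it need be.

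Second, the condition may be a sensible caution, because it applies where the chi-square approximation is weakest. That also stands as an observation, and the table above bears it out. It argues for a better p-value rather than for no test. A Cox hazard ratio would have no finite estimate with an empty arm, but the SAP plans no Cox model.

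Third, a reader might infer that the plan loses its efficacy comparison, or a large share of its power. The documents support neither. The unconditional analyses answer the same question, and in the Kaplan-Meier analysis subjects who withdraw alive "will be censored at the date of their last evaluation", so their follow-up is kept. No significance level or success rule is attached to the log-rank test, so counting an unrun test as a failure to reject has no meaning here. Nor do the background figures supply a matched power contrast: the 93.3% for the related product in Protocol 2.1.6.2 is EvFS, and the 66% for matched unrelated donors in Protocol 2.1.3.1 is OS.

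Fourth, the condition might be read as requiring an event in OTL-101 and in all control groups, so that no deaths among matched-related-donor controls would cancel the primary comparison. The rest of the sentence describes pairwise comparisons, so that reading is strained. It is worth closing off, but not worth sizing.

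**Conclusion.** The point holds as a minor defect. The condition is stricter than the log-rank test requires, and it drops the planned test if OTL-101 has no events. At assumed true rates of 95% to 99% that happens with probability 36% to 82%.

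The loss is small. The other comparisons remain, and the primary efficacy objective in Protocol 3.1 is to estimate survival. The condition cannot inflate a claim for OTL-101, since it only removes a test in the most favourable case.

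That the test is computable does not depend on the assumed rates. The probabilities do, and the example p-values depend on the assumed control numbers and event times. Protocol 2.1.6.2 does not say how long the 18 patients had been followed, so their result shows that an empty arm is realistic and does not establish the 12-month outcome.

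**What to change.** In SAP 8.3.1.1, replace the condition with: if there is at least one event in the two groups being compared combined, at a time when both have subjects at risk. State that it applies to each pairwise comparison separately, for OS and EvFS at 12 and 24 months.

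Require an exact or permutation log-rank p-value when events are few or one group has none, and define few in advance. Compute it with follow-up cut at the analysis time point, because permuting group labels presumes similar censoring in the two groups.

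The cost is a sentence or two in the SAP and a short addition to the analysis code, with no new data. The protocol sentence can stand, since it defers to the SAP.

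There is one small downside. Protocol 14.5 says that no data are masked, and Protocol 2.1.6.2 shows that outcomes were partly known, so relaxing the condition admits a test whose likely direction can be foreseen. The documents do not show whether the primary analysis had already been run. The SAP should record the date of the change and, if it follows the primary analysis, label the test post hoc.

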11.2 Design Considerations and Data

This is a subject-level historically controlled, prospective, non-randomized Phase I/II clinical trial to assess the safety and efficacy of autologous transplantation of CD34+ cells originated from the bone marrow of ADA-SCID infants and children following human ADA cDNA transfer by the EFS-ADA lentiviral vector.

Descriptive results will be presented for the study cohort.

Comparisons will be made to three cohorts:

- 1) A historical control group consisting of ADA-SCID HSCT-treated subjects lacking a medically eligible HLA-matched sibling/family donor and treated at GOSH/UCL (UK) or Duke University Children's Hospital, North Carolina Transplant Center (USA) from the year 2000 onward
- 2) A historical control group consisting of ADA-SCID HSCT-treated subjects having a medically eligible HLA-matched sibling/family donor and treated at GOSH/UCL (UK) or Duke University Children's Hospital, North Carolina Transplant Center (USA) from the year 2000 onward
- 3) All HSCT-treated subjects from GOSH/UCL or Duke University Children's Hospital, who were treated with HSCT from the year 2000 onward, with any type of donor

Details on the historical HSCT control groups from GOSH/UCL and Duke University Children's Hospital can be found in [Appendix H](#).

Statistical analyses will be performed, and their outcomes presented, in three stages:

- Interim look – 6 months
 - Descriptive statistics for all available subjects
- Primary analysis - Comparison on primary efficacy endpoints to the HSCT control cohorts—12 month follow-up analysis
 - Descriptive statistics for the complete study cohort, with all patients having reached at least 12 month follow-up
 - Comparison to HSCT control cohorts on safety, primary efficacy endpoints and need of immunoglobulin replacement (IgRT) (main secondary efficacy endpoint).
- End of study analysis:
 - Descriptive statistics for the complete study cohort, with all patients having completed the study (24-month follow-up)
 - Comparison to HSCT control cohorts on safety, primary efficacy endpoints and need of immunoglobulin Replacement (IgRT) (main secondary efficacy endpoint).

In each study stage and for all analyses, all relevant data available will be used.

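### The 12-month Kaplan-Meier and log-rank analyses have no 12-month cut, so later events can enter the test, and at end of study it is the same test as the 24-month log-rank

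*SAP*

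**What the plan says.** The primary efficacy endpoints are overall and event-free survival at 12 months (SAP 5.1; Protocol 11.3.2).

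SAP 8.3.1.1 defines the time variable thus: "Overall survival will be evaluated using the time in months from transplant to either the subject's death or their last evaluation". For controls without dates it is "age in months at death/end of follow-up - age in months at transplant". Neither definition stops at month 12. The one censoring rule given for the Kaplan-Meier curve is that "any subject who withdrew from the study prior to 12 months and was known to be alive at the last evaluation will be censored", with the last evaluation as the censoring date. Nothing is said about subjects who are followed, or have an event, after month 12.

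The section also asks for the 12-month Kaplan-Meier proportion, "along with the median survival time (and interquartile range), if they can be estimated from the data". The test follows, on condition that each group has at least one event: "the log-rank test will be used to compare the difference in survival curves". The event condition has no time limit.

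SAP 8.3.1.2 applies the same method to event-free survival. SAP 8.3.2.1 says: "Overall and event-free survival at 24 months will be summarized in the same way as for the analyses at 12 months". Protocol 11.2 adds: "In each study stage and for all analyses, all relevant data available will be used". Protocol 11.6.2.4.1 describes Kaplan-Meier curves with a log-rank test, again without a horizon, and lists the 12-month rates as a separate item.

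Under SAP 6, the primary analysis takes place once all subjects have 12 months of follow-up and the end-of-study analysis once all have 24. Overall and event-free survival are compared with the controls at both.

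**The concern.** A log-rank test compares whole curves over the period in which both groups are at risk. With no cut, the test under the 12-month heading covers a longer and uneven period. At the primary analysis, subjects treated early have already been followed past month 12. At end of study the period reaches about 24 months.

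This has three consequences:

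- The 12-month proportion and the 12-month log-rank can point in different directions, because only the second counts later events.
- The log-rank for a 12-month endpoint can change between the primary and end-of-study analyses although no 12-month outcome has changed.
- At end of study, 8.3.1.1 and 8.3.2.1 yield one and the same test, reported once as a 12-month and once as a 24-month result.

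The event condition adds to this. A single OTL-101 event after month 12 can switch on a 12-month test that the 12-month data alone would not allow.

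**Working it through.** **The plan's own figures.** The documents give no power, alpha or event count for the log-rank. The only design figures are the precisions in Protocol 11.4 for a proportion with N = 20 (7% with no failure, 12% with one). The exact two-sided 95% interval for 19/20 is 0.751 to 0.999, a half-width of 12.4%, which agrees. For 20/20 it is 0.832 to 1, a half-width of 8.4%; 7.0% results only from a one-sided 95% bound. This point does not depend on either figure.

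**Inputs from the documents.** There are 20 OTL-101 subjects, each followed for 24 months (Protocol 1.1, 11.4). Protocol Appendix H identifies 25 controls at GOSH and 10 at Duke, of all donor types. The number without a matched related donor is not given.

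**Assumed data.** OTL-101 has 20 subjects with one event, at month 5, so the event condition is met. There are 24 controls with six events, at months 2, 3, 4, 6, 7 and 9. All others are event-free, with OTL-101 followed to month 24 and controls for longer.

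**Formula.** With one event at each event time, E = Σ n_T/n and V = Σ (n_T/n)(n_C/n), where n_T and n_C are the numbers at risk on OTL-101 and control and n is their sum. O is the number of OTL-101 events, and chi-square = (O − E)²/V on 1 df.

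| Month | n_T | n_C | Event in | n_T/n | V term |
|---|---|---|---|---|---|
| 2 | 20 | 24 | control | 0.4545 | 0.2479 |
| 3 | 20 | 23 | control | 0.4651 | 0.2488 |
| 4 | 20 | 22 | control | 0.4762 | 0.2494 |
| 5 | 20 | 21 | OTL-101 | 0.4878 | 0.2499 |
| 6 | 19 | 21 | control | 0.4750 | 0.2494 |
| 7 | 19 | 20 | control | 0.4872 | 0.2498 |
| 9 | 19 | 19 | control | 0.5000 | 0.2500 |

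1. Cut at 12 months: O = 1, E = 3.346, V = 1.745. Chi-square = (1 − 3.346)²/1.745 = 3.15, p = 0.076.
2. Uncut, with control events added at months 14 (19 and 18 at risk; 0.5135, 0.2498) and 18 (19 and 17 at risk; 0.5278, 0.2492): E = 4.387, V = 2.244, chi-square 5.11, p = 0.024. Cutting at 24 months gives the identical result.
3. Uncut, with a second OTL-101 event at month 15 instead (19 and 18 at risk): O = 2, E = 3.859, V = 1.995, chi-square 1.73, p = 0.19.

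In all three cases 19/20 (95%) and 18/24 (75%) are event-free at month 12, a difference of 20 points. Only the log-rank moves. Adding control events at months 30 and 40 to case 2 leaves chi-square at 5.11, because no OTL-101 subject is then at risk.

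**The event condition.** Assume 20 against 20, with the only OTL-101 event at month 18.1 and six control events, four of them by month 12. Uncut, the condition is met and the test gives p = 0.036. Cut at 12 months, OTL-101 has no event and no test is run.

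**How often it matters.** In simulations of 3,000 trials per setting, with 10, 20 or 30 controls, OTL-101 had 5% events by month 12 and 0 or 5% in months 12 to 24. Controls had 30 to 40% by month 12 and 5 to 10% after. A test not run counted as not below 0.05. Whether p fell below 0.05 differed between the uncut and the 12-month-cut test in about 11 to 33% of trials. Where OTL-101 had 5% late events, about 22 to 25% of trials ran the test only because of an event after month 12. Whenever the uncut test ran, it equalled the 24-month test. All these rates are assumptions.

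**The case against.** The strongest reply is that the full curve is intended. Protocol 11.6.2.4.1 lists Kaplan-Meier with log-rank and the 12-month rates as two separate analyses, and aims at as full a picture as a small sample allows. The median in SAP 8.3.1.1 also needs the whole curve. A fixed-time proportion beside a full-follow-up log-rank is a common pairing. This explains the protocol text. It does not explain two SAP sections that present one identical test as both a 12-month and a 24-month analysis.

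A second reply is that the test may never run. Protocol 2.1.6.2 reports no death and no failure event in 18 evaluable patients at March 2016. This stands. With no OTL-101 event, the missing cut makes no difference to the test.

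A third is that crossing 0.05 depends on the example. This also stands. With four control events by month 12 (months 2, 4, 6 and 9) and one OTL-101 event at month 6.1, p is 0.22 cut and 0.076 after adding control events at months 14 and 18.

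A reader might infer that events after month 12 drive the primary result, or that the log-rank supplies the primary p-value. The documents do not support either. The primary objective is to estimate survival by 12 months, no alpha or decision rule is attached to the log-rank, and the 12-month proportions come first in 8.3.1.1. Nor can the effect be shown with examples that have no OTL-101 event, since the SAP's own condition would stop the test.

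**Conclusion.** The point holds, within limits. As written, the 12-month log-rank for overall and event-free survival has no 12-month horizon. Events up to about month 24 enter it and can decide whether it runs and what it shows. At end of study it coincides with the 24-month test by construction.

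Not affected are the 12-month proportions with their exact intervals and difference, the Kaplan-Meier 12-month estimate and, read in context, the Bayesian 12-month rates. Control events after about month 24 add nothing.

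The identity with the 24-month test follows from the text alone. The size does not: the p-values of 0.076, 0.024 and 0.19 rest on assumed event times and an assumed 24 controls, and 0.05 is only a yardstick. With so few events expected, one or two late ones are enough to matter. The SAP should be changed, but the main 12-month estimates are sound without the change.

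**What to change.** In SAP 8.3.1.1 and 8.3.1.2, state that for the 12-month log-rank every subject in every group who is still event-free at 12.0 months is censored at that time, and that the condition of one event per group is judged on events within that window. In 8.3.2.1, say the same for 24.0 months. Keep the uncut curve and the median as descriptive.

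This takes a sentence or two in the SAP, minor programming and no new data. The 12-month test will have fewer events. Events just after month 12 will count only in the 24-month analysis. Examples are a PEG-ADA restart following the month-12 visit, which has a window of 4 weeks either side (Protocol 6.4.1, 8.4), and events in controls timed only by age in months, for whom the boundary is also less exact. The later data are not lost, because the 24-month test uses them.
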